### **Sample Teeth Clinical Findings**

GCF was taken from the 5 deepest pockets measured before the treatment from the patients in the SP and P groups of the study groups before the treatment, on the 15th and 30th days after the treatment. GCF was taken from 5 randomly selected teeth with  $GI=0$   $PI=0$  and  $PD \leq 3$  from individuals in SH and H groups.

All clinical parameters (PI, GI, BOP, PD, CAL and GCF volume) of these selected teeth were analyzed statistically. There was a significant difference between the groups in all clinical parameters before treatment. The measurements of SP and P groups were higher than the healthy groups ( $p<0.05$ ).

There was a significant difference between the groups in terms of BOP, PD, CAL and GCF volumes on the 15th and 30th days after treatment.

There was no statistically significant difference between the periodontitis groups (SP-P) and healthy groups (SH-H) on the 0th, 15th and 30th days in terms of smoking ( $p>0.05$ ).

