### **Study Protocol and Statistical Analysis Plan**

Before the study, One Way ANOVA test with a significance level of 5% was used for the sample size calculation. Based on this analysis, the sample size was determined as at least 11 people in each group and a total of 44 subjects to detect a difference between groups. This cross-sectional study was approved by Ondokuz Mayıs University Clinical Research Ethics Committee (OMUKAEK) Samsun, Turkey (protocol number; 2019/324).

Fourty four individuals, 22 males and 22 females who were older than 18 were enrolled in the study. The study groups were selected according to the following criteria from individuals who applied to the Ondokuz Mayıs University Faculty of Dentistry Periodontology Department Clinic for treatment or control, accepted to participate in the study, were systemically healthy, did not take any medication in the previous 6 months, and did not receive periodontal treatment in the previous 6 months:

Group 1: (SP) Stage 3 Grade C patients (n:11)

Group 2: (P) Stage 3 Grade A patients (n:11)

Group 3: (SH) Periodontally healthy smokers (n:11)

Group 4: (H) Non-smokers with periodontally healthy (n:11)

Individuals were included as smokers if they had smoked  $\geq 10$  cigarettes/day for  $\geq 5$  years, whereas individuals were included as nonsmokers if they had no previous history of smoking. The periodontitis stage III patients were evaluated clinically and radiographically, and were selected to have teeth with CAL  $\geq 5$  mm in at least 30% of them. Exclusion criterias were as follows; patients under the age of 18, pregnant or lactating women, patients who have a history of with systemic disease or cancer or chemotherapy and radiotherapy or ongoing drug therapy who might be affect the clinical characteristics of periodontitis, patients who smoke less than 10 cigarettes/day or who quit smoking.

In order to standardize the study, all radiological and clinical examinations were performed by a single investigator. In clinical examination, Plaque Index (PI), Gingival Index (GI), bleeding on probing (BOP), probing depth (PD) and clinical attachment loss (CAL) scores were measured and recorded from 6 regions of each tooth (buccomesial, midbuccal,

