buccodistal, linguo/palatomesial, midgingual/palatal, linguo/palatodistal regions) with using using millimetric (mm) calibrated University of North Carolina (UNC) (Hu-Friedy, Chicago, Illinois, USA). And up-to-date panoramic radiographs were taken from all patients on the day of the examination to determine periodontal status. After the clinical and radiographic evaluations, the participants were asked to come for GCF sample and treatment 1 day after the clinical evaluations, since bleeding may occur during probing.

From the patients in the SP and P groups, GCF samples were obtained from the 5 deepest pockets before the treatment, on the 15th and 30th days after the treatment. GCF samples were obtained taken from 5 randomly selected teeth with GI=0 PI=0 and SPD  $\leq 3$  from healthy individuals in the SH and H groups.

GCF samples were acquired by intrasulcular technique from selected pockets. Before sampling, the sites were isolated with cotton rolls, saliva and supragingival plaque were removed by cotton pellets, if present. Standardized filter paper strips (Peripaper® Oraflow Inc. New York, USA) were placed in the pocket for 30 seconds. Strips contaminated with blood or saliva were discarded. The absorbed GCF volume was measured with a precalibrated Periotron 8000 instrument (PeriotronR 8000, Pro Flow Inc., Amityville, NY, USA). Then, the strips were placed in sterile 0.5 ml Eppendorf (Eppendorf AG, Hamburg, Germany) tubes. Eppendorf tubes were stored at -80°C in Ondokuz Mayıs University Faculty of Medicine Department of Biochemistry until ELISA analysis. GCF samples were converted to an actual volume ( $\mu$ L) by reference to a standard curve.

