### **Treatment and Follow-up Protocol**

Patients in the SH and H groups were advised to come for routine controls by not applying any periodontal treatment. However for patients in the SP and P groups, non-surgical periodontal treatment was applied as full mouth debridement protocol in a single session, after the GCF samples were collected from selected pockets.

The periodontitis patients were called again on the 15th and 30th days after the treatment. First of all, the GCF sampling process was repeated from the teeth whose GCF sample was collected before. Then, clinical examination parameters (PI, GI, BOP, PD and CAL) values were measured again and recorded.

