### **Statistical analysis**

SPSS for Windows Ver. for statistical analysis and graphics. 22.0 (SPSS Inc., Chicago, ILL, USA) and MS-Excel 2016 programs were used. Statistical significance level was accepted as p<0.05.

The normal distribution of the data in our study was evaluated with the Shapiro-Wilks test. The mean±standard deviation was used for the descriptive statistics for the normally distributed variables, and the median (min-max) value for the non-normally distributed variables. While examining the distribution of the gender variable in the groups, the result of the Chi-Square test was evaluated.

OneWay ANOVA test was applied to the variables showing normal distribution in the comparison of the data between groups. In post-hoc analyses, homogeneously distributed data according to Levene variance homogeneity test were evaluated with Tukey test, and data that were not homogeneously distributed were evaluated with Tamhane T2 test. Variables that did not show normal distribution were evaluated with the Kruskal-Wallis test. Bonferroni corrected Mann-Whitney U test was used in order to determine the group that caused the difference in the variables with a significant difference as a result of the Kruskal-Wallis test.

Paired-Sample T Test and Repeated Measured Analysis of Variance were used for the variables showing normal distribution in the evaluation of the within-group changes according to time. Significant differences as a result of analysis of variance were examined with Bonferroni, one of the multiple comparison tests. Variables that did not show normal distribution were analyzed with the Friedman test. The Wilcoxon test was used to determine the group that caused the difference in the variables with a significant difference as a result of the Friedman test.

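### In the periodontitis groups, the probing that picks the 5 deepest pockets appears also to be their day-0 depth, so part of any fall at the sampled sites is regression to the mean

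*Combined protocol and SAP*

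**What the plan says.** - **Pool of sites.** In the opening section, PD and CAL "scores were measured and recorded from 6 regions of each tooth", and "all radiological and clinical examinations were performed by a single investigator". No repeat reading and no intra-examiner error is reported.
- **Selection.** For SP and P, "GCF samples were obtained from the 5 deepest pockets before the treatment, on the 15th and 30th days after the treatment". The Sample Teeth Clinical Findings section confirms that depth was judged before treatment: "GCF was taken from the 5 deepest pockets measured before the treatment from the patients in the SP and P groups".
- **Baseline.** After the examination, "the participants were asked to come for GCF sample and treatment 1 day after the clinical evaluations, since bleeding may occur during probing". That second visit is described as GCF collection followed by debridement. No further probing is mentioned.
- **Follow-up.** Under Treatment and Follow-up Protocol, GCF is taken on days 15 and 30 from the teeth sampled before, and then the clinical parameters, PD and CAL included, "values were measured again and recorded". Both periodontitis groups are treated.
- **Analysis.** The Sample Teeth section says that all clinical parameters "of these selected teeth were analyzed statistically". For change over time within a group, the Statistical analysis section names paired t-tests and repeated-measures ANOVA where a variable is normal, with Friedman and Wilcoxon tests for non-normal variables. Neither section mentions the way the sites were chosen.

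**The concern.** The largest few of many error-prone readings overstate the true depth of the sites they pick out, because sites whose error happened to be positive are more likely to be picked. When the same sites are read again, that excess disappears whether or not treatment worked. Here the selecting reading appears to serve as day 0, while the day-15 and day-30 readings play no part in selection. A before-after comparison at these sites therefore mixes treatment response with a fall produced by the selection.

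The sampled sites also supply the GCF, so their PD change is the natural clinical companion to the changes in periostin and IL-17A. An inflated fall would make the clinical side of that pairing look stronger than it is. The design has no untreated periodontitis patients or sites, and no replicate baseline, from which the size of the artefact could be estimated.

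**Working it through.** **The plan's own figures.** There is none to reproduce on this point: the documents give no PD or CAL values, no between-site spread and no probing error. From the documents come 6 sites per tooth, 5 selected pockets, 11 patients per group and a 5% significance level. Everything else below is assumed.

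**Direction.** Write a reading as true depth plus error, with between-site SD *s* and error SD *e*. For normally distributed depths, the expected fall on a second reading with no true change is

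fall = [e² / (s² + e²)] × (mean first reading of selected sites − mean of all sites).

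This is positive whenever *e* > 0 and the selected sites lie above the mean. Example with s = 1.5, e = 0.5 and overall mean 4.0 mm, where the 5 deepest of 150 simulated sites average 8.10 mm on first reading: [0.25 / (2.25 + 0.25)] × (8.10 − 4.0) = 0.10 × 4.10 = 0.41 mm. Simulation with right-skewed depths and readings rounded to 1 mm gives 0.33 mm for the same setting. The formula is thus a guide to sign and order of size only.

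**Simulation with zero treatment effect.** Assumed: 26 teeth × 6 = 156 sites, mean PD 3.8 mm, gamma-distributed true depths, independent normal reading error, rounding to 1 mm. The 5 deepest sites on reading 1 are compared with an independent reading 2 of the same sites.

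| Between-site SD (mm) | Fall, error SD 0.4 | Fall, error SD 0.6 | Fall, error SD 0.8 |
|---|---|---|---|
| 1.2 | 0.32 mm | 0.55 mm | 0.86 mm |
| 1.5 | 0.23 mm | 0.43 mm | 0.69 mm |
| 1.8 | 0.19 mm | 0.35 mm | 0.54 mm |

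A paired t-test on 11 patients gives p<0.05 in about 45% to 100% of such trials (88% at the middle setting), against a nominal 5%. The full-mouth mean, which involves no site selection, falls by 0.00 mm.

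**Sensitivity.**
1. *Unit of analysis.* The text speaks of selected teeth. If the six sites of each selected tooth are averaged, the fall under the same inputs is about 0.03 to 0.15 mm, with rejection in about 9% to 46% of trials (17% at the middle setting).
2. *Patient-level variation between visits.* The table assumes none. An assumed shift of SD 0.3 mm lowers single-site rejection to roughly 28% to 99%. At the middle setting it drops to about 67%, or to about 49% with SD 0.5 mm. The mean fall is not removed.
3. *Wider inputs.* With 25 teeth, mean 4 mm, site SD 1.0 to 2.0 mm and error SD 0.3 to 1.0 mm, the fall is 0.11 to 1.46 mm for single sites (rejection 23% to 100%) and 0.02 to 0.21 mm for whole-tooth means. Taking the deepest pocket on each of five different teeth gives 0.12 to 1.44 mm.

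**CAL** was not simulated. Selection is on depth, so CAL inherits only the error it shares with PD.

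**The case against.** The best reply is that the documents do not report the result at risk. The Sample Teeth section gives only between-group findings. The significant decrease over time in both periodontitis groups stands under Full Mouth Clinical Findings, where no sites were selected. The Statistical analysis section is generic and does not say that the time tests were run on sampled-site PD. This stands, and it makes the point conditional.

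The premise also rests on silence: a brief text mentions no second probing, which does not prove that none took place. That stands as well, although no other source of a day-0 value is described. The single examiner is not an answer, because one examiner removes between-examiner differences but leaves that examiner's own reading error.

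A reader might go further and infer any of the following. The documents support none of them.
- *The sampled-site fall would be significant even if treatment did nothing.* Rejection is frequent under many settings but far from certain, and it drops sharply with whole-tooth averaging or with visit-to-visit variation.
- *The reported clinical improvement is an artefact.* The reported falls are full-mouth.
- *SP versus P is biased.* Both groups follow the same rule, so a bias would need a different pocket distribution or probing error, and none is shown.
- *The gap to the healthy groups at day 0 is spurious.* Comparing the deepest pockets with teeth no deeper than 3 mm builds that gap in. A modest excess in the deep readings does not change its meaning.
- *The biomarker results are distorted.* GCF measures were not used to select sites, and no effect on them is shown.

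**Conclusion.** The concern holds in a limited form. One described pre-treatment probing, selection of the extremes on it and unselected follow-up readings together push the sampled sites' day-0 PD upward relative to days 15 and 30. Any within-group fall at those sites therefore includes some regression to the mean, and CAL probably does to a lesser degree. The direction follows from the design, provided that the selecting reading is indeed the day-0 value.

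The size cannot be derived from the documents. Under the stated assumptions it is about 0.2 to 0.9 mm for single sites and about 0.03 to 0.15 mm for whole-tooth means, and the test would reject more often than its nominal 5%. This is a directional bias in a supporting outcome. It is no ground for doubting the full-mouth response or for saying that treatment had no effect.

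**What to change.** **Design.** Separate selection from baseline. At the treatment visit, after the GCF strips are taken and before debridement, have the same examiner re-measure PD and CAL at the 5 sampled sites. Use that reading, not the selecting one, as the sampled-site day-0 value. A reading that played no part in selection has an expected artefact of zero, and probing after the strips keeps bleeding out of the GCF sample. State also whether the single sites or whole-tooth means are analysed.

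**Cost.** Five extra site readings in each of 22 patients (5 × 22 = 110 sites) at a visit that already takes place, and a slightly smaller apparent improvement.

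**Data already collected.** The extra reading can no longer be taken. Do not present sampled-site PD or CAL change from day 0 as treatment response without stating that it includes regression to the mean. Keep the treatment-response conclusion on the full-mouth values, where the text already places it. If a second pre-treatment reading does exist, say so and use it as day 0. This costs wording only.

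### At day 0, PI, GI and PD of the sampled teeth are tested between groups after being used to choose those teeth, so the healthy-group smoking comparison on PI and GI is empty and the diseased-healthy contrasts are not independent evidence

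*Combined protocol and SAP*

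**What the plan says.** The sampling rule is in the opening section, *Study Protocol and Statistical Analysis Plan*, and again in *Sample Teeth Clinical Findings*.

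- Healthy groups (SH smokers, H non-smokers): "GCF samples were obtained taken from 5 randomly selected teeth with GI=0 PI=0 and SPD" of at most 3. No unit is given; I take it as mm. The results section calls the same limit PD.
- Periodontitis groups (SP, P): "GCF samples were obtained from the 5 deepest pockets before the treatment". The results section confirms that depth was judged on the pre-treatment measurement: "GCF was taken from the 5 deepest pockets measured before the treatment from the patients in the SP and P groups". No PI or GI condition applies to these sites.

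The same section then states: "All clinical parameters (PI, GI, BOP, PD, CAL and GCF volume) of these selected teeth were analyzed statistically". For day 0 it reports: "There was a significant difference between the groups in all clinical parameters before treatment", with SP and P above the healthy groups (p<0.05). On smoking it reports: "There was no statistically significant difference between the periodontitis groups (SP-P) and healthy groups (SH-H"), covering days 0, 15 and 30 (p>0.05).

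*Statistical analysis* specifies ANOVA or Kruskal-Wallis across groups. For non-normal variables the pairs are compared by Bonferroni-corrected Mann-Whitney, at a level of 0.05. Nothing there treats the selection variables differently from the others.

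**The concern.** Three of the six variables tested on the sampled teeth (PI, GI, PD) are the ones that decided which teeth could be sampled. A test on a variable fixed or bounded by selection partly or wholly returns the selection rule.

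Two statements are at stake. The first is the disease difference at the sampled sites, where PI, GI and PD are listed as findings alongside variables that the rule does not fix. The second is the absence of a smoking difference in the healthy groups. Smoking is one of the two factors that define the four groups, so a null statement about it will be read as substantive. In SH and H, any tooth with plaque or gingival inflammation was barred from the sample, so a smoking effect on either could not have appeared there.

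**Working it through.** **Inputs.** Group size is 11, 44 in total (opening section). Alpha is 0.05 (*Statistical analysis*). The documents give no test statistic or exact p-value for the sampled-tooth tests, so there is no figure of theirs to reproduce. The sample-size calculation states neither power nor effect size, and nothing below depends on it.

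**Assumptions.** One value per participant is analysed, tests are two-sided, and Bonferroni covers the 6 pairs among four groups. The tested day-0 values come from the same examination that served for selection; only one pre-treatment examination is described.

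**1. PI and GI, SH versus H.** Every value is 0 by rule. With n1=n2=11 and N=22, Mann-Whitney U = 121/2 = 60.5, exactly its null mean. With t tied values the variance is

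(n1·n2/12)·[(N+1) − (t³−t)/(N(N−1))].

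With t=22: (10648−22)/462 = 23, and 23−23 = 0. The variance is zero; the recomputed test returns p=1.0 and a t-test is undefined. No smoking effect of any size could change this.

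**2. PD, diseased versus healthy.** Healthy values cannot exceed 3; diseased values are each patient's deepest. If every selected pocket exceeds 3 mm, the two groups of a pair separate completely and the exact p-value is

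2 / C(22,11) = 2/705432 = 2.8e-6, or 1.7e-5 after multiplying by 6.

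The condition is an assumption, because no PD threshold is stated for SP or P.

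**3. PI and GI, diseased versus healthy.** The healthy side sits at the floor, so a difference can only go upward. Significance depends on k, the number of the 11 patients in a diseased group with a non-zero value. Taking the non-zero values as distinct, U − 60.5 = 5.5k, and t = 22−k in the variance above (normal approximation, no continuity correction).

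| k | z | p | p × 6 |
|---|---|---|---|
| 5 | 27.5/11.18 = 2.46 | 0.0139 | 0.084 |
| 6 | 33.0/11.95 = 2.76 | 0.0058 | 0.035 |
| 11 | 60.5/14.25 = 4.25 | 0.00002 | 0.0001 |

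The four-group Kruskal-Wallis test, with k non-zero values in each diseased group, gives p=0.080 at k=3 and p=0.024 at k=4. So the rule fixes the direction, while significance still needs observed non-zero values in SP and P: about 6 of 11 for a corrected pair.

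**4. PD, SH versus H.** The cap removes sites above 3 but leaves room below it. I used a simulation with assumed inputs: H mean 1.8 mm, between-person SD 0.3, between-site SD 0.5, five sites per person, truncated at 3 mm, 2000 runs.

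| Shift in SH before truncation | Detected at 0.05 | Detected at 0.05/6 |
|---|---|---|
| 0.3 mm | 39% | 13% |
| 0.5 mm | 79% | 43% |
| 0.8 mm | 99% | 91% |

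The comparison is restricted, not decided in advance.

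**The case against.** The strongest reply is that these are baseline descriptors of sampling sites, that the selection rule is stated just before the tests, and that *Full Mouth Clinical Findings* reports the same day-0 pattern for PI, GI, BOP, PD and CAL on data not tied to the five sampled teeth. No conclusion on periostin, IL-17A or IL-17E rests on these p-values. All of that stands and limits the consequence. It does not rescue the SH-H statement on PI and GI, which carries no caveat and could not have come out otherwise.

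Three stronger readings are tempting, and the documents do not support them.

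- A reader might infer that the whole SH-H null is built in, PD included. It is not: PD can differ below the cap (step 4), and the rule does not directly fix BOP, CAL or GCF volume.
- A reader might infer that the diseased-healthy PI and GI results carry no information. SP and P sites were chosen on depth alone, so significance there reflects observed plaque and inflammation. For days 15 and 30 the same section lists group differences in BOP, PD, CAL and GCF volume but not in PI or GI. The plan describes recall of periodontitis patients only, so the healthy comparators then are apparently still the day-0 zeros. The omission is not an explicit null result, but it fits the view that the zero floor alone does not secure significance.
- A reader might extend the point to full-mouth CAL, because the stage III patients "were selected to have teeth with CAL" of 5 mm or more in at least 30% of teeth. That gap restates the definition of diseased and healthy groups. The threshold is a floor with no ceiling, and nothing shows that it narrows SP-P differences.

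**Conclusion.** The point holds for the day-0 sampled-tooth tests of PI, GI and PD, with a different force for each contrast:

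- SH-H on PI and GI: empty, p=1 by construction. This needs only that the selection rule was applied as written.
- Diseased-healthy on PD: selection-driven in practice, p=2.8e-6 per pair if all selected pockets exceed 3 mm.
- Diseased-healthy on PI and GI: direction forced, so not independent evidence; significance still depends on the SP and P data (about 6 of 11 non-zero, assuming six pairs and one value per participant).
- SH-H on PD: range-restricted only.
- SP-P: not affected by the zero rule.

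This is a fault of analysis and reporting with limited reach. It withdraws an empty null result and some non-independent p-values; the full-mouth disease and smoking results remain available.

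**What to change.** In *Sample Teeth Clinical Findings*:

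1. Report day-0 PI, GI and PD of the sampled teeth descriptively, as a check that site selection worked. Give no diseased-healthy or SH-H p-values for them, and say that they were selection variables.
2. Limit the day-0 SH-H smoking statement for sampled teeth to BOP, CAL and GCF volume.
3. Rest any healthy-group smoking statement on PI, GI and PD on the results in *Full Mouth Clinical Findings*.
4. Keep the SP-P comparisons, and keep the group tests of BOP, CAL and GCF volume.

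The cost is a few fewer p-values and some rewording. The data needed are already collected.
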